7.3 Verification of Inclusion/Exclusion Criteria

After the consent process is complete, trained study personnel will review the Inclusion and Exclusion criteria with the subject/LAR. The following options are then possible:

- If the subject meets all criteria, they will be allowed to proceed with the study.
- If the subject fails to meet criteria, no further study-related procedures will be conducted.
- If the failure to meet criteria is minor, the investigator may choose to approach the Medical Monitor for a waiver. A waiver will be granted only if doing so will not place the subject at increased risk if allowed to participate in the study.

Study personnel will document the review of Inclusion and Exclusion Criteria on the appropriate form and place the signed form in the study file. The investigator will be notified of the results of the review.

7.4 Randomization and Blinding

- 7.4.1 A randomization schedule will be created and maintained by the UAMS Research Pharmacy.
- 7.4.2 Subjects who agree to participate in the study and meet inclusion and exclusion criteria will be assigned to the next available treatment. The UAMS Research Pharmacy will track enrollment and randomize blinded treatments for administration to properly enrolled research subjects.
- 7.4.3 The UAMS Research Pharmacy will deliver the blinded investigational treatment to the study personnel who will administer the drug to the subject.

7.5 Screening Study Procedures

7.5.1 Screening and Enrollment Log

All subjects who provide informed consent will be entered into the screening and enrollment log. Once screening is complete, the log will be updated to identify those subjects who pass screening and proceed into the dosing phase of the trial.

7.5.2 Review of Head CT Exam

The investigator will review the CT of the head with the treating physician (if not the investigator) or radiologist to assure that the subject meets the

eligibility criteria. The CT must be negative for severe hemorrhage or severe hemorrhagic stroke. This will be documented in the study record.

7.5.3 Medical History

A brief medical history reviewing information pertinent to the study will be completed by the investigator. The medical history will be documented and signed by the investigator (physician).

7.5.4 Physical Exam

A brief, targeted physical exam will be completed by the investigator to document the subjects condition and assure that there are no obvious reasons that it would not be in the best interest of the subject to proceed with the study. Weight will be measured in light clothing without shoes and recorded in the study record. Physical findings will be documented and signed by the investigator (physician).

7.5.5 Concomitant Medications

All medications currently taken by subjects will be reviewed and documented on the appropriate form. The form will be included in the study file.

7.5.6 Pregnancy Test

A serum pregnancy test will be performed on all women of child-bearing potential. Dosing with DDFPe will not begin before the test confirms that the women are not pregnant. If the test indicates that a woman is pregnant, she will be immediately dropped from the study.

7.5.7 NIH Stroke Scale

The NIHSS will be administered during Screening to assure that subjects score between 2 and 20, inclusive, to meet the study Inclusion criteria. Initial NIHSS scores from outside originating hospitals or facilities are acceptable only if performed by a certified neurologist. The NIHSS will be repeated throughout the study as indicated in the Schedule of Time and Events (Appendix 4). The NIHSS may be found at:

https://www.ninds.nih.gov/doctors/NIH_Stroke_Scale.pdf

7.5.8 ECG

A 12-lead ECG will be performed as part of the Screening process to assure that subjects with serious arrhythmias are appropriately excluded from the study. The ECG will be inspected by the treating physician and the investigator. If a serious rhythm disturbance is observed, a cardiologist may be consulted to confirm the findings. If confirmed by the cardiologist, the subject will be withdrawn from the study prior to administration of DDFPe. After the study is completed, all ECGs will be reviewed by a board certified cardiologist to confirm that no new arrhythmias developed during the course of treatment.

7.5.9 Laboratory Studies

All subjects will have the following laboratory tests collected prior to receiving DDFPe:

- Complete Blood Count
- Electrolytes (Na, K, Cl₂)
- BUN
- Creatinine
- LFTs (AST, ALT, Total Bilirubin, Direct Bilirubin, Albumin)
- Calcium
- Glucose

It is anticipated that many of these tests will be done as part of the subjects' routine care. These tests will provide baseline values prior to administration of DDFPe for later comparison with post-dosing test results. The results of these tests may or may not be available prior to dosing with DDFPe. None of the tests would exclude a subject from participating in the study.

7.6 Day 1: Study Procedures

After documentation that the subject passed the screening procedures and meets all Inclusion and Exclusion criteria, study personnel will check to assure that a patent intravenous catheter is in place for infusion of the DDFPe. The catheter should be used solely for infusion of DDFPe and compatible intravenous fluids during the study intervention period (from the initiation of Dose #1 to after the Dose #3 infusion is complete).

Dose #1: DDFPe will be ordered from the pharmacy and prepared as previously described. The time that the infusion begins will be recorded. The drug or placebo will be infused over 5-10 minutes. At the end of the infusion, the time will again be recorded. Vital signs and pulse oximetry will be monitored. Measurements will be recorded every 15 minutes. The subject will be observed for any signs of adverse events for 90 minutes after the completion of the infusion.

Dose # 2: Any new concomitant medications will be recorded. The second dose of DDFPe or placebo will be administered as previously described over 5-10 minutes. Times will be recorded at the beginning and end of the infusion as before. Vital signs and pulse oximetry will be monitored. Measurements will be recorded every 15 minutes. The NIHSS will be repeated within 60 minutes after the end of the DDFPe infusion. The subject will be observed for any signs of adverse events for 90 minutes after the completion of the infusion.

Dose #3: Any new concomitant medications will be recorded. The third dose of DDFPe or placebo will be administered as previously described over 5-10 minutes. Times will be recorded at the beginning and end of the infusion as before. Vital signs and pulse oximetry will be monitored. Measurements will be recorded every 15 minutes. The NIHSS will be repeated within 60 minutes after the end of the DDFPe

infusion. The subject will be observed for any signs of adverse events for 90 minutes after the completion of the infusion.

Vitals should be taken at all scheduled time points (i.e. every 15 minutes); however, deviations from scheduled times will not be considered protocol deviations. The exact date and time of each measurement will be recorded on the CRF.

Post-Dose #3: Approximately 4 ± 1 hours after the end of Dose #3, the following observations will be made:

- Concomitant medications administered after Dose #3
- A brief physical examination
- Vital signs (BP, HR, RR)
- Pulse oximeter measurement
- NIHSS
- ECG
- Laboratory testing

Any AEs observed during the intervention period will be recorded, assessed, and followed to resolution.

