5.3.2 Dose Limiting Toxicity

Dose limiting toxicity (DLT) will be defined by the following criteria:

- Clinically significant changes in vital signs:
 - Heart rate \pm 50% from baseline
 - Respiratory rate >30 /min
 - Systolic blood pressure < 90 mmHg or >220 mmHg
 - Diastolic blood pressure >110 mmHg
- New (i.e. not seen at baseline) ECG changes consistent with:
 - Acute right ventricular dilation or strain
 - Incomplete or complete bundle branch block
 - Q waves in leads III and aVF
 - T-wave inversion and/or ST segment changes in the precordial leads
 - Any other clinically significant cardiac arrhythmia
- Common Terminology Criteria for Adverse Events (CTCAE) 4 Grade 3 or higher cough, dyspnea, chest pain-cardiac or non-cardiac, chest wall pain or hypoxia (See [Appendix 1](#) for specific criteria)
- NIHSS: sudden worsening of 4 or more from the baseline (pre-DDFPe initiation)
- The Medical Monitor will review all data collected at Post-Dose #3 (approximately 4-6 hours after the end of the Dose #3 infusion of DDFPe or placebo for each subject). Enrollment will be on hold until the Medical Monitor has reviewed the data and approves enrollment of an additional subject. The Medical Monitor may choose to temporarily halt the study if serious concerns arise regarding subject safety.

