5.3.3 Maximum Tolerated Dose

The algorithm for determining the MTD is as follows:

- Up to six subjects and two controls will be enrolled at each dose level constituting each cohort. Subjects will be evaluated for four hours after receiving the last of the three doses and again at discharge from the hospital or one week later, whichever is sooner.
- DLT is previously defined in [Section 5.3.2](#).
- If no DLTs are observed in a patient at Post-Dose #3 of DDFPe or placebo the Medical Monitor may allow progression to the next patient.

- After all 8 subjects have been enrolled in a cohort, the Medical Monitor will review the data. A decision as to whether the study may proceed to the next cohort will be made.
- If a total of two or fewer subjects in an 8 subject cohort experience a DLT, escalation to the next cohort may proceed if approved by the Medical Monitor. If three or more DLTs were observed, the Medical Monitor may consult with the Research Pharmacist to determine if the observed DLTs occurred in subjects who received DDFPe or placebo. If any of the DLTs were observed in the subjects receiving placebo, the Medical Monitor may allow the study to proceed as long as two or fewer subjects with DLTs received DDFPe.
- If three or more subjects who received DDFPe in an 8 subject cohort experience a DLT, the MTD will be determined to have been exceeded and further enrollment in the cohort as well as dose escalation will stop. The dose administered to the previous cohort will be considered to be the MTD.
- Subjects who withdraw from the study for reasons other than a DLT may be replaced.
- The Medical Monitor will review all safety data for each patient and cohort and must grant approval before proceeding to the next patient and/or cohort.
- Exploration of lower dose levels intermediate to a level previously shown to be well tolerated may be considered. In addition to reducing the dose, this might include reducing the number of doses, increasing the time between doses, and/or altering the infusion time.
- The dose exploration will be complete when either: (1) the MTD has been defined or (2) when no MTD has been reached but six subjects and two controls have been treated at the last cohort level approved by the Medical Monitor.

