Appendix 4: Schedule of Time and Events

	Day 1					Day 4	Day 7±1 or Day of Discharge	Day 30 ±7	Day 90 ±14
Study Procedures	Screening (Baseline)	Dose #1 ^a	Dose #2 ^a	Dose #3 ^a	Post- Dose #3 ^b				
Informed Consent	X								
I/E Criteria	X								
Concomitant Meds	X	X	X	X	X				
Medical History ^c	X						X	X	X
Physical Exam ^c	X				X		X	X	
Weight	X								
Vital Signs ^d	X	X	X	X	X		X	X	
Pulse Oximetry ^e	X	X	X	X	X		X		
Modified Rankin Scale	X						X	X	X
NIHSS	X		X ^f	X ^f	X		X	X	
ECG ^g	X				X		X		
Pregnancy Test ^h	X								
Lab Studies ⁱ	X				X		X		
Administer DDFPe ^j		X	X	X					
Adverse Events		X	X	X	X	X	X	X	X

a Each dose of DDFPe or placebo is to be administered intravenously over 5-10 minutes. Start and stop times will be recorded as will the volume infused.

b Post-dose #3 concludes approximately 4-6 hours after the end of the Dose #3 infusion.

c Brief, targeted medical history and physical exam.

d Vital signs (blood pressure, heart rate, respiratory rate) will be done every 15 minutes through the end of Post-Dose #3 (approximately 4-6 hours) and then consistent with standard procedures for the hospital unit. Temperature will be done every 1-4 hours consistent with the hospital unit standard procedures.

e Continuous or spot readings may be taken; if continuous readings are used, record the measurement every 15 minutes.

f To be performed within 60 minutes following the dose.

g 12-lead ECG to be examined at the bedside by the study personnel and later reviewed by a board certified cardiologist.

h Serum pregnancy test will be done in pre-menopausal women.

i To include: CBC, electrolytes (Na, K, Cl), BUN, creatinine, LFTs, calcium, albumin, glucose

j DDFPe or placebo to be administered over 5-10 minutes intravenously through a peripheral or central IV. The interval between the end of one dose and the beginning of the next should be 90 ± 10 minutes.

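### No NIHSS is scheduled between Dose 1 and Dose 2, and no rule requires the section 5.3.2 DLT criteria to be checked before a subject is re-dosed

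*Combined protocol and SAP*

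**What the plan says.** Section 5.3.2 defines DLTs by vital signs, new ECG changes, selected CTCAE events of Grade 3 or higher, and the stroke scale: "NIHSS: sudden worsening of 4 or more from the baseline (pre-DDFPe initiation").

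For Dose 1, section 7.6 provides vital signs and oximetry, then a period of observation: "Measurements will be recorded every 15 minutes. The subject will be observed for any signs of adverse events for 90 minutes". For Doses 2 and 3 it adds an NIHSS no later than an hour after the infusion ends. Appendix 4 agrees: the NIHSS is marked at Screening, Dose 2, Dose 3, Post-Dose #3, Day 7 or discharge, and Day 30, but not at Dose 1.

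DLTs act as a gate in two places in section 5.3.3. Between patients: "If no DLTs are observed in a patient at Post-Dose #3 of DDFPe or placebo the Medical Monitor may allow progression". Between cohorts, the mandatory stop begins "If three or more subjects who received DDFPe in an 8 subject cohort experience a DLT"; with two or fewer DLTs, "escalation to the next cohort may proceed if approved by the Medical Monitor".

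Within one subject, section 5.6.3 requires the product to be stopped for life-threatening progression, for adverse events judged unacceptable, at the subject's wish, or when the investigator sees unacceptable risk. Section 6.4 lists further grounds on which the investigator may stop it. Section 7.1 lets the treating physician end study procedures. None of these refers to section 5.3.2.

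**The concern.** The protocol names a neurological criterion for dose-limiting toxicity and measures it after the second and third doses, but not after the first exposure. It gives no reason for the difference. A subject whose score has worsened by 4 points after Dose 1, without staff recognising it as such, can receive Dose 2 with no scheduled score to show it. Section 7.2 allows subjects with aphasia, confusion or impaired consciousness to enrol through a representative. For them, self-report is a weaker substitute for a scored examination.

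The second part is the decision rule. An NIHSS is done between Dose 2 and Dose 3, but nothing says that it, or any other 5.3.2 criterion, must be looked at before Dose 3 is given. The DLT definition governs the next patient and the next cohort, not the next dose in the same subject.

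What is at stake is mainly subject safety. DLT capture comes second: a worsening after Dose 1 that had eased by the time of the first score could go uncounted.

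**Working it through.** The plan states no figure to reproduce; section 10.1 says that no sample size was estimated. The check is of the schedule, using the protocol's own windows.

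**Inputs**
- Infusion time: 5 to 10 minutes per dose (section 7.6).
- Gap from the end of one infusion to the start of the next: 90 ± 10, so 80 to 100 minutes (section 5.5; Appendix 4, footnote j).
- NIHSS after Doses 2 and 3: 0 to 60 minutes after the infusion ends (section 7.6).
- Vital signs: every 15 minutes (section 7.6).
- Subjects: up to 24, with 6 on DDFPe and 2 on placebo per cohort (Study Summary; section 3.1).

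**1. What is scheduled before Dose 2.** Dose 2 starts 5 + 80 = 85 to 10 + 100 = 110 minutes after Dose 1 starts. In the gap there are 80/15, rounded down to 5, to 100/15, rounded down to 6, vital-sign readings. There are no NIHSS scores.

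**2. Time to the first NIHSS after baseline, from the start of Dose 1.**
- Earliest: infusion 1 + gap + infusion 2 + 0 = 5 + 80 + 5 + 0 = 90 minutes.
- Latest: 10 + 100 + 10 + 60 = 180 minutes.

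In both cases two of three doses have been given.

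**3. What is scheduled before Dose 3.** The NIHSS after Dose 2 is due by 60 minutes and Dose 3 starts no earlier than 80, so one score is available. No text makes Dose 3 depend on it.

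**4. Whether a score after Dose 1 fits.** Under the same 60-minute limit, 80 − 60 = 20 minutes remain before the earliest permitted Dose 2, and 100 − 60 = 40 before the latest. The first score would then come 5 + 0 = 5 to 10 + 60 = 70 minutes after Dose 1 starts.

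**5. How many courses a hold could affect.** Three or more DDFPe subjects with a DLT means that the MTD has been exceeded. In a full cohort that passes, at most 2 of 6 DDFPe subjects have one, and the courses of at least 6 − 2 = 4 are untouched.

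**6. Extra assessments.** 24 × 1 = 24 NIHSS, plus one for each replacement subject.

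**The case against.** The strongest reply is that within-subject protection already exists. Section 5.6.3 is mandatory, and an investigator who recognises a DLT can treat it as an unacceptable event or risk; section 6.4 and the treating physician's power in 7.1 add to this. That stands. A reader might infer that nothing stops the next dose after a recognised DLT, and the documents do not support that reading. What is missing is a link: the terms in 5.6.3 are left to judgement, are not tied to 5.3.2, and cannot help with a worsening that nobody scored.

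A second reply is that the criterion is a sudden worsening, and that subjects are observed in a unit used to stroke care (section 8.7). Many such events would probably be seen. But the protocol does not rely on observation alone after Doses 2 and 3, and gives no reason to do so after Dose 1.

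Third, more measurement against a fixed stop at three DDFPe subjects can only raise the number of DLTs found. For illustration, with six subjects and assumed detected DLT rates, the chance of three or more is 9.9% at a rate of 20% and 25.6% at 30%. The documents give no basis for either rate, or for how far one added NIHSS would move it. The direction is a fair cost to name.

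Fourth, DLTs carry no causality requirement, and section 5.3.3 foresees some on placebo. Automatic withholding would cut courses short for events of the stroke itself. This stands, and is why the fix below holds the dose for a decision and does not forbid it.

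**Conclusion.** The point holds as a specific gap with a cheap remedy. One of the DLT criteria has no scheduled measurement between Dose 1 and Dose 2. The first score comes 90 to 180 minutes after Dose 1 starts, with two of three doses given. No stopping rule is tied to section 5.3.2, and no DLT check is required before Dose 2 or Dose 3. These times assume that infusions, gaps and NIHSS stay within the stated windows.

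The documents give no basis for the share of DLTs that would be missed, or for any net effect on the MTD. A reader might infer that the MTD is biased; that cannot be shown from them.

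A reader might also infer that ECGs between doses are needed, since new ECG changes are DLTs ("New (i.e. not seen at baseline) ECG changes consistent with") and the first ECG after baseline is at Post-Dose #3, when all doses have been given. The schedule is as described, but the documents do not establish that need. Heart rate is recorded every 15 minutes, usual care may include physiological monitoring (section 7.1), and serial 12-lead ECGs would be an added procedure. They are an option for the sponsor to weigh, and the conclusion does not depend on them.

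**What to change.** 1. In section 7.6 and Appendix 4, add an NIHSS no later than 60 minutes after the end of Dose 1, on the same terms as after Doses 2 and 3.

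2. In sections 5.6.3 and 7.6, state a rule such as:

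> Before Dose 2 and before Dose 3, the criteria in section 5.3.2 are reviewed on the measurements available by then. If any has been met since the start of Dose 1, the next dose is held, and is given only if the investigator and the Medical Monitor agree that it is safe. The subject counts as having a DLT in either case and stays in follow-up.

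The rule should not ask for a repeat reading to confirm a DLT: section 5.3.2 has no such requirement, and adding one would change the primary endpoint.

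**Cost.** At most 24 extra NIHSS assessments, plus one per replacement subject, with a scale already used after the later doses. The added score also serves the exploratory objective on immediate response (section 2.3). The Medical Monitor must be reachable during dosing, and the protocol should say what happens if a held dose passes the 100-minute limit. Slightly more DLTs may be found against the fixed stop, and some subjects with a DLT may not complete the three-dose course whose MTD is sought. Withholding a dose does not lower the DLT count, because the algorithm counts subjects and such a subject is already counted.

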7.7 Day 4: Study Procedures

All subjects will be contacted to assess AEs. If the subject is still hospitalized, any significant change in condition will be recorded as a possible AE and assessed by the investigator. All AEs will be graded (mild, moderate, severe), assessed for relatedness (not related, possibly related, probably related, definitely related), and followed to resolution as described in Section 8.0.

In the event that the subject has been discharged from the hospital before Day 4, subjects or their LAR will be contacted by telephone. AEs will be assessed and followed as described above.

7.8 Day 7 ± 1 (or Hospital Discharge Day): Study Procedures

The subject will be re-examined on the day of discharge or at one week (Day 7 ± 1), whichever comes first. At this visit, the following procedures will be completed:

- A brief interval medical history
- A brief physical examination
- Vital signs (BP, HR, RR)
- Pulse oximeter measurement
- NIHSS
- ECG
- Laboratory testing
- Modified Rankin Scale

Any AEs observed during the intervention period will be recorded, assessed, and followed to resolution.

If subjects are discharged before Day 7, they will be contacted by telephone to assess possible AEs seven days after administration of the investigational product. If any possible AEs are identified, they will be assessed and followed as previously described.

7.9 Day 30 (±7 days): Study Procedures or Telephone Follow Up

This visit will occur as part of the routine, clinically indicated follow up. If no routine appointment is scheduled, the subject may be contacted by telephone to complete the study visit. At this visit, the following procedures will occur:

- Interval medical history
- A brief physical examination (omitted for telephone follow up)
- Vital signs (BP, HR, RR) (omitted for telephone follow up)
- mRS
- NIHSS (omitted for telephone follow up)
- Adverse Events

7.10 Day 90 (±14 days): Office Visit or Telephone Follow Up

This visit will occur as part of the routine, clinically indicated follow up. If no routine appointment is scheduled, the subject may be contacted by telephone to complete the study visit. The purpose of this visit is to assess longer term complications and functioning related to stroke. At this visit, the following procedures will occur:

- Interval medical history
- mRS
- Adverse Events

The medical history will focus on additional cardiovascular events that may have occurred since the stroke, any changes in functioning at 90 days compared with pre-stroke.

